After the patient has received oral information and signed a written informed consent, characterization of the patient material will be made. The study will be conducted in four phases. The first week they use their usual blanket (baseline). Sleep, fatigue, anxiety, and depression will be recorded with the scales mentioned above. Then a second part follows four weeks when they use the blanket randomized to (Week 2-5). In the second phase, patients are randomized to either get a 6 or 8 kg lining blanket or a lightweight cover of approximately 1.5 kg of the same appearance in which light plastic chains are sewn in. This cover is of such low weight that it corresponds to a regular blanket and therefore acts as a placebo control. Randomization and instruction, as well as collection of blankets after four weeks of use, will be carried out by a person who does not perform the ratings at inclusion and follow-up. Patients should maintain their medication unchanged during the study period. They are followed up by telephone every week. At the telephone interview information about how they used the blanket will be gathered, and patients will estimate their sleep with the scales mentioned above. After four weeks of use of the blanket, the final visit for the randomized study will be conducted, and data (scales and actigraph) from this visit is the primary outcome of the study.

In the third phase, all patients are offered an open-follow up study in a 4-week (week 6-9) where they can choose freely between ball and chain weighted blankets. After these four weeks, everyone is called for a second visit with new estimates and collection of actigraph data of (week 9). In the fourth phase, patients who wish to continue with one of the weighted blankets will be offered to do so. After 12 months, patients who choose to continue using weighted blankets will be contacted by telephone to check the extent to which they use the blanket and are asked to estimate the same symptoms as before.

Power Calculation

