In a previously uncontrolled pilot study of weighted-duty non-control groups, the average sleep time decreased from 98 minutes (SD 69) to 31 minutes (SD 28). Based on these results, calculating the effect of the blanket for a future study where the placebo deck had no effect, and the active blanket would have the same effect as in the pilot study figures would want a power of 0.9 with a significance level of 0.05, only 15 subjects would be required in the study. However, we have no data on the effect of sleep on sleep measured with the ISI scale. Nor is it likely that the placebo blanket would not have any effect at all. However, we expect that patient material of about 100 individuals should be enough to find a significant effect.

Statistical analysis

Comparison between the effect on the groups will be performed after four weeks and eight weeks with conventional methods of statistical significance testing in controlled and randomized studies. All patients who used the blanket for at least one night will be included in the analysis (equivalent to "intention to treat"). Data from patients who discontinue treatment will be asked if they can accept to participate in follow-up in the same way as if they had completed treatment. In these cases, data are included in the analysis as measured. Secondly, Last Observation Carried Forward (LOCF) or other established statistical method is used to handle data from patients who interrupt treatment.

Self-assessed values before, after eight weeks and 12 months will be analyzed with and at eight weeks after with paired t-test for dependent variables. When data distribution does not match normal distribution, the analysis will be supplemented by non-parametric tests.

Timetable

The study will extend over three years.

Safety monitoring

Clinical monitoring will be done by treatment staff on the Affective section in consultation with the patient.

Ethical considerations

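### The 12-month ratings come only from patients who chose to keep a weighted blanket, so the uncontrolled paired analysis of them is open to selection bias and cannot show a lasting effect

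*Protocol*

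**What the plan says.** All places are in the protocol.

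- **Procedure, third phase (weeks 6–9).** Patients choose freely among the weighted blankets. At the end, "everyone is called for a second visit with new estimates and collection of actigraph data".
- **Procedure, fourth phase.** Entry is by the patient's own wish: "patients who wish to continue with one of the weighted blankets will be offered to do so". The last follow-up is then restricted: "After 12 months, patients who choose to continue using weighted blankets will be contacted by telephone". These patients are asked how much they use the blanket and "are asked to estimate the same symptoms as before". No 12-month rating is described for anyone else.
- **Statistical analysis, between groups.** "Comparison between the effect on the groups will be performed after four weeks and eight weeks". No group comparison is planned at 12 months.
- **Statistical analysis, within patients.** "Self-assessed values before, after eight weeks and 12 months will be analyzed", and the method named is the "paired t-test for dependent variables", with non-parametric tests added if the data are not normal. Words appear to be missing from this sentence, probably through translation, so it does not show which time points form the pair.
- **Patients.** Everyone who accepted inclusion and received a blanket is to be analysed.
- **Inclusion and exclusion criteria.** Entry requires an ISI score of at least 14.

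**The concern.** Continuing after the open phase is partly an outcome. A patient who feels better by week 9, for whatever reason, has more cause to keep the blanket than one who does not. Rating only continuers at 12 months therefore conditions the result on how patients were doing earlier. Several of the eligible diagnoses, such as bipolar disorder and recurrent depression, can run in episodes, so some continuers may simply have been in a good period.

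The question on extent of use has the same limit. It is put only to people who had elected to use a blanket, so it cannot give persistence among all who were randomised.

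What is at stake is the meaning of the 12-month result. A significant paired test in this group could be taken as evidence that the effect lasts. A later analysis plan cannot repair this, because the Procedure section fixes who is contacted and the missing ratings would never be collected.

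**Working it through.** The plan gives no figure on this point, so there is none to reproduce. The check asks how far self-selection alone can move a paired test.

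**Inputs.** From the protocol: about 100 patients (Power Calculation) and significance level 0.05. The level is taken as two-sided, so the nominal rate of false improvement is 2.5%. Assumed, because the protocol does not give them:

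- true mean change from baseline of zero at week 9 and at 12 months, with equal SD
- share continuing, f: 50%, 70% or 90%
- link s between a patient's inclination to continue and the week-9 change: 0.3 to 0.6
- correlation r between week-9 and 12-month change: 0.3 to 0.7

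**Baseline versus 12 months.** The fraction f with the strongest inclination continue. With z = Φ⁻¹(1−f) and λ = φ(z)/f, in units of the SD of change:

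- spurious mean improvement = r·s·λ
- variance among continuers = 1 − (r·s)²·λ·(λ−z)
- rejection rate from the noncentral t with n = 100f

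Strongest case in the range (f = 0.5, s = 0.6, r = 0.7): λ = 0.798 and z = 0. The bias is 0.7 × 0.6 × 0.798 = 0.335. The variance is 1 − 0.1764 × 0.637 = 0.888, so the SD is 0.942. Noncentrality is 0.335/0.942 × √50 = 2.52, which gives 69%.

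Weakest case (f = 0.9, s = r = 0.3): λ = 0.195. The bias is 0.09 × 0.195 = 0.018, the SD is 0.999 and noncentrality is 0.17, which gives 4%.

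| Continuing | s 0.3, r 0.3 | s 0.6, r 0.5 | s 0.6, r 0.7 |
|---|---|---|---|
| 50% | 0.07 SD, 7% | 0.24 SD, 40% | 0.34 SD, 69% |
| 70% | 0.04 SD, 6% | 0.15 SD, 24% | 0.21 SD, 44% |
| 90% | 0.02 SD, 4% | 0.06 SD, 8% | 0.08 SD, 12% |

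A simulation of 4,000 trials per scenario agrees to within about 3 percentage points. If s = 0, r = 0 or everyone continues, the bias is zero and the rate is about 2.5%. Rating all 100 patients also brings it back to about 2–3%.

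**Eight weeks versus 12 months.** The eight-week point is the week-9 visit. Continuers' mean week-9 change is s·λ and their mean 12-month change is r·s·λ, so the pair shows a worsening of (1−r)·s·λ. At f = 0.5, s = 0.6, r = 0.5 this is 0.5 × 0.6 × 0.798 = 0.24 SD, the same size as the spurious improvement above but in the opposite direction.

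**What rating everyone leaves in place.** Regression to the mean from the ISI threshold equals (1 − reliability) × SD × h, where h is the normal density divided by the upper tail probability, both taken at (14 − mean)/SD. Assume SD 5, population mean 12–18 and reliability 0.6–0.8. The smallest value is 0.2 × 5 × 0.368 = 0.37 ISI points and the largest 0.4 × 5 × 1.069 = 2.14. With n = 100, false significant improvement from this source alone runs from 22% to above 99%.

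**The case against.** A reader might infer that the 12-month test is bound to show lasting improvement. The protocol does not support that, for three reasons.

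- **The pair is not identifiable.** Baseline versus 12 months is a fair reading. Eight weeks versus 12 months is a natural contrast for durability, and there the bias runs the other way.
- **The size depends on unknowns.** If exactly the patients with the best week-9 change continued (s = 1, SD of ISI change 6, 90 patients at week 9, 50–70% continuing, r = 0.5), the spurious gain would be 1.5–2.4 points and false significance 54–81%. That is close to a worst case. Patients may also stop for reasons such as discomfort, and more than 70% may continue.
- **Selection is not the only source of apparent improvement.** Regression to the mean and natural recovery act as well, and may matter more.

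It can also be said that the stakes are small. The primary outcome is the four-week randomised visit, no stated aim or hypothesis concerns 12 months, and asking continuers about use is a legitimate adherence check. All of this stands, and it limits the weight of the point.

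The last defence is that the Statistical analysis section asks patients who discontinue treatment to accept follow-up and allows LOCF. That text follows the four- and eight-week comparison and does not mention 12 months, and declining an optional fourth phase is arguably not discontinuing. If non-continuers were meant to be covered, the Procedure section contradicts it. The defence does not remove the flaw.

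**Conclusion.** The flaw is real and fixed by the plan: 12-month ratings are collected from a self-selected group and placed in an uncontrolled paired analysis. If continuing follows perceived benefit and change persists to some degree, a comparison of baseline with 12 months is biased towards improvement. Under the assumed inputs, false significance lies between about 4% and 69% against a nominal 2.5%. Only the direction is firm, and only for that pair and under those two conditions. The size cannot be determined from the protocol.

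Two further inferences are not supported. The point does not touch the randomised four-week result. Nor would contacting everyone make the 12-month test evidence of durability, since that removes only the selection part.

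**What to change.** 1. **Procedure.** Contact all randomised patients at 12 months, whether or not they continued, with the same ratings and a question on current blanket use.
2. **Statistical analysis.** Name the pair of time points compared. Summarise change in all randomised patients and give the proportion still using a blanket out of all randomised.
3. **Reporting.** With no control at 12 months and an ISI threshold at entry, present the 12-month change as descriptive and not as evidence of a lasting effect.
4. **If non-continuers are not called.** Drop the 12-month significance test. Label the ratings as those of patients who chose to continue, with the denominator, and show week-9 scores for continuers and non-continuers. Week 9 already covers everyone, so this needs no new data.

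The cost is one extra telephone call per non-continuer, a line in the protocol and in the consent form, and probably a less favourable 12-month figure.

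### Fifteen subjects in total do not give 90% power for the two-group comparison described: under equal allocation and a two-sided unadjusted test they give about 62%, and 28 to 30 are needed

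*Protocol*

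**What the plan says.** The Power Calculation section of the protocol starts from an uncontrolled pilot in which "the average sleep time decreased from 98 minutes (SD 69) to 31 minutes (SD 28" minutes being the unit throughout. It carries these figures into a hypothetical controlled trial, "for a future study where the placebo deck had no effect, and the active blanket would have the same effect" as in the pilot, and states: "would want a power of 0.9 with a significance level of 0.05, only 15 subjects would be required in the study".

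The Procedure section describes that controlled trial: "patients are randomized to either get a 6 or 8 kg lining blanket or a lightweight cover of approximately 1.5 kg". The Statistical analysis section plans a comparison between the groups.

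The Power Calculation section then steps back from its own figure. It notes that "we have no data on the effect of sleep on sleep measured with the ISI scale", and that a wholly inert placebo blanket is unlikely. It ends: "we expect that patient material of about 100 individuals should be enough to find a significant effect". No calculation is given for the 100.

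**The concern.** The sentence ties a power of 0.9 to a total number of subjects, and the scenario it describes has two arms. A standardized difference of about 1.27 is very large, but 15 patients split over two arms leave only seven or eight in each. That looked too few for 90% power.

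This is the only power figure in the protocol. If it is wrong, a reader who sets the planned 100 against the stated 15 sees a margin of 100/15, nearly sevenfold, where the like-for-like margin is about 100/30, a little over threefold. What is at stake is the accuracy of that statement, not the adequacy of the trial.

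**Working it through.** **Inputs from the protocol (Power Calculation)**
- Placebo group: mean 98, SD 69 (stays at the pilot's baseline, because placebo is taken to do nothing).
- Active group: mean 31, SD 28 (as at the end of the pilot).
- Power 0.9, significance level 0.05.

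**Assumed, because the protocol does not state them:** two-sided test, 1:1 allocation, comparison of follow-up values without baseline adjustment.

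**Standardized difference**
- Difference = 98 − 31 = 67 minutes.
- Root-mean-square SD = √[(69² + 28²)/2] = √[(4761 + 784)/2] = √2772.5 = 52.65.
- d = 67/52.65 = 1.272.

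**Can the stated 15 be reproduced as a total?** With groups of 8 and 7, the noncentrality is d·√(8·7/15) = 1.272 × 1.932 = 2.46 on 13 degrees of freedom (two-sided critical value 2.160). Power is 0.624. The Welch test, which allows for unequal SDs, gives 0.618. So 15 in total is not reproduced.

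**What 90% requires.** The noncentrality is d·√(n/2) on 2n − 2 degrees of freedom:

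| n per group | Total | Power, t-test | Power, Welch |
|---|---|---|---|
| 13 | 26 | 0.875 | 0.860 |
| 14 | 28 | 0.900 (0.8997) | 0.887 |
| 15 | 30 | 0.920 | 0.910 |

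The requirement is therefore 28 to 30 in total. The normal approximation, 2(1.960 + 1.282)²/1.272² = 12.98, gives 13 per group, or 26 in total.

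**Would another choice make 15 a sufficient total?**
- *One-sided test:* power is 0.753 with 15 in total. For 90%, 12 per group are needed (0.915), or 24 in total.
- *Best unequal allocation (Welch, two-sided):* 15 in total reaches at most 0.693. For 90%, 25 in total are needed (0.911).
- *Baseline adjustment:* replace d by d/√(1 − r²), with 12 degrees of freedom. Power with 15 in total is 0.741 at r = 0.5, 0.884 at r = 0.70 and 0.901 at r = 0.72. So 15 would suffice at a baseline-to-follow-up correlation of about 0.72 or more. The protocol gives no correlation and mentions no such adjustment.

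**Calculations that do return 15**
- *Per group:* 14 to 15, as in the table.
- *One group, before/after, uncorrelated measurements:* SD of the change = √(69² + 28²) = 74.46, so the effect is 67/74.46 = 0.900. With n = 15 the noncentrality is 0.900 × √15 = 3.48 on 14 degrees of freedom, and power is 0.899.

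**Sensitivity only.** If the active group also had SD 69, then d = 67/69 = 0.971. Power is 0.896 at 23 per group and 0.909 at 24, so 48 in total. This sets aside the SD of 28 that the protocol reports under the active blanket.

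**Planned size.** With 50 per group, power in the pilot scenario exceeds 0.999 (0.998 in the sensitivity case).

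**The case against.** The strongest case on the other side is that nothing depends on the 15. The protocol presents it as a hypothetical, gives two reasons not to rely on it, and plans about 100 patients instead. That stands, and it is why the point is minor. It does not make the sentence correct.

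The document is also a translation, and the English of this paragraph is visibly damaged. Since 15 per group reproduces almost exactly, the Swedish text may have been right and the words for per group lost. That is possible. It cannot be shown from the text at hand, and an English-language reader has only the sentence as it stands.

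The test's sidedness, the allocation ratio and any baseline adjustment are not stated either. Of these, only baseline adjustment with a correlation of about 0.72 or more would make 15 a valid total, and nothing in the protocol supplies that figure.

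Three stronger readings are tempting and not supported:
- *That the 15 is a per-group number mislabelled as a total.* The before/after calculation fits as well, so the origin cannot be settled.
- *That the true requirement is 48, and the stated total a third of it.* That replaces the protocol's own active-group SD of 28 with 69. On the stated inputs the shortfall is about half.
- *That the trial is too small, or that the 100 needs rework because of this error.* The planned size far exceeds 30, and exceeds 48 as well. The lack of a calculation behind the 100 is a separate matter of detail that a statistical analysis plan may hold.

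**Conclusion.** The sentence is wrong as written, and the point is minor. For the placebo-controlled comparison it describes, 15 patients in total give about 62% power, not 90%. The requirement is 14 to 15 per group, 28 to 30 in total, so the stated total is about half of what is needed. This rests on the pilot means and SDs as printed, and on the assumed equal allocation, two-sided test and absence of baseline adjustment. A one-sided test lowers the requirement to 24, still well above 15.

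Confidence is high that 15 in total does not follow from an unadjusted two-group test. No conclusion is drawn about how the figure arose.

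**What to change.** In the Power Calculation section, restate the hypothetical requirement as *about 15 per group, 30 in total (two-sided, equal allocation)*. If the author's records show that the 15 came from a one-group before/after calculation, delete the sentence, because that calculation belongs to a different design. A check against the Swedish text would show whether the words for per group were lost in translation. Leave the planned size at about 100.

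The cost is one edited or deleted sentence. No patients are added, and the analysis does not change.

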Research plan, translated from Swedish, including a statistical analysis plan

A controlled study of weighted chain blankets

Document Date: November 1, 2015

Scientific description

Purpose

The primary aim is to investigate whether the nightly use of a weighted chain blanket has a significantly better effect on sleep time, total sleep time and daytime fatigue for patients with sleep disturbance in psychiatric disease compared to a light chain blanket (equivalent to placebo) after four weeks of use. Secondary issues are whether treatment with weighted chain blanket results in a significantly better effect than a light blanket for objectively measured sleep and subjectively assessed anxiety, depression, and pain.

Hypotheses

The use of the weighted chain blanket allows:

1. Sleep time decreases.
2. Sleep stays longer with fewer wake-ups during the night.
3. The sleep becomes calmer
4. The sleep becomes less tense
5. Pain decreases daytime
6. Pain decreases at night
7. Anxiety and anxiety decrease daytime
8. Anxiety and anxiety decrease at night
9. Fatigue decreases daytime
10. Concentration capacity increases daytime

Primary outcome measures

The patient's subjective symptoms of sleep and day fatigue will be evaluated by the Insomnia Sleep Inventory (ISI) and the Fatigue Scale Inventory (FSI) scales. It will also be evaluated by the patient's self-assessed values in the self-assessment rating scale developed by Stockholm Utility for evaluating ball and chain blankets (hereafter referred to as "rating scale for weighted blankets"). Depression and anxiety will be evaluated with the scale Hospital Anxiety and Depression Scale (HAD). Objective sleep parameters will be recorded with actigraphs.

Chief researcher

Responsible for the study of patients with bipolar disorder and/or ADHD is [name], leg. Occupational Therapist at the Affective Section, Psychiatry Southwest of Stockholm County Council (SLSO) and [name], Medical Doctor and Chief Physician and Section Manager at the Affective Section, Psychiatry Southwest in Stockholm County Council (SLSO)

Overview

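### The week-4 randomised comparison fixes neither the test nor the use of baseline, although baseline scale scores are collected; ANCOVA on those scores would protect power and close the choice

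*Protocol*

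**What the plan says.** The title describes the document as "Research plan, translated from Swedish, including a statistical analysis plan". Under Procedure, patients spend the first week with their own blanket as a baseline, and in that week "Sleep, fatigue, anxiety, and depression will be recorded with the scales mentioned above". Actigraphy in the baseline week is not mentioned. After four weeks on the randomised blanket there is a final visit, and "data (scales and actigraph) from this visit is the primary outcome of the study".

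Under Statistical analysis, "Comparison between the effect on the groups will be performed after four weeks and eight weeks", using "conventional methods of statistical significance testing in controlled and randomized studies". That is all the Protocol says about the method for the randomised comparison. The only test it names applies to self-assessed values over time (before, at eight weeks and at 12 months), which are analysed "with paired t-test for dependent variables". A further sentence adds: "When data distribution does not match normal distribution, the analysis will be supplemented by non-parametric tests". The non-parametric test is not named, and it is unclear whether that sentence reaches the group comparison.

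Under Power Calculation, the Protocol says it has no effect data on the ISI scale and expects about 100 patients to be enough.

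**The concern.** The week-4 group comparison is the main analysis, yet several different tests satisfy its description: a t-test on week-4 scores, a t-test on change from baseline, ANCOVA, or a rank test. On the same data they can give different answers. Two things are at stake.

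The first is precision. Power on ISI has not been calculated, so with about 100 patients precision should not be given away. A test that ignores baseline discards information the trial already holds and leaves any chance baseline difference between the arms in the estimate.

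The second is prespecification. If the test is picked once results are visible, the nominal 5% error rate no longer holds.

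**Working it through.** **The plan's own figure.** Power Calculation gives 15 subjects for power 0.9 at 0.05, from a fall in sleep time from 98 (SD 69) to 31 (SD 28) minutes. The difference is 98 − 31 = 67 and the averaged SD is √((69² + 28²)/2) = √2772.5 = 52.7. A two-sided, unadjusted two-sample t-test then needs 15 per arm (power 0.92). Read as a two-arm total, 15 gives about 0.62. A one-sample paired t-test with within-patient correlation between 0 and 0.2 needs 16 to 14 patients. So the figure fits more than one test and does not show which one is planned. It also says nothing about ISI.

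**Inputs for the comparison.** From the Protocol: about 100 patients and a significance level of 0.05. Assumed, because the Protocol does not give them: 1:1 allocation (50 per arm), a two-sided test, a true difference d = 0.5 SD of the week-4 score, and baseline-to-week-4 correlation r = 0.3, 0.5 or 0.7.

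**Power.** Noncentral t with noncentrality d√(50/2) = 5d for the unadjusted test. ANCOVA multiplies the residual variance by 1 − r², so d becomes d/√(1 − r²) and one degree of freedom is lost (97 instead of 98).

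| | r = 0.3 | r = 0.5 | r = 0.7 |
|---|---|---|---|
| Variance factor 1 − r² | 0.91 | 0.75 | 0.51 |
| Effective d with ANCOVA | 0.524 | 0.577 | 0.700 |
| Power, unadjusted week-4 test | 0.70 | 0.70 | 0.70 |
| Power, ANCOVA | 0.74 | 0.82 | 0.93 |
| Equivalent gain in patients, 1/(1 − r²) − 1 | 10% | 33% | 96% |
| Difference detectable at 90% power (unadjusted 0.65 SD) | 0.62 SD | 0.57 SD | 0.47 SD |

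The power gain is about 4, 12 and 24 percentage points. With d = 0.4 it is about 4, 12 and 28; with d = 0.6, about 3, 8 and 14.

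**Chance imbalance.** The baseline difference between arms has standard error √(2/50) = 0.20 SD. An imbalance of that size shifts an unadjusted week-4 difference by about r × 0.20, that is 0.06, 0.10 or 0.14 SD. ANCOVA removes this shift.

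**Open choice of test.** In 10,000 simulated null trials per value of r (50 per arm, normal data, equal SDs at both times), each of four admissible tests (week-4 t, change t, ANCOVA, Mann-Whitney) alone had a type I error of about 5%. Reporting the smallest of the four p-values gave 9.4%, 10.7% and 10.7% at r = 0.3, 0.5 and 0.7. This is the worst case of selection, for one scale only.

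**The case against.** **ANCOVA already fits the text.** A reader might infer that the plan rules out baseline adjustment and therefore loses power. The Protocol does not support that. Adjustment is neither planned nor excluded, ANCOVA is itself a conventional method, and speaking of an effect on the groups can be read as referring to baseline. This stands: the loss arises only if an adjusted model is not the one used.

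**The size rests on an unknown r.** This also stands. Entry at ISI 14 or more narrows the baseline range and can lower r, so for ISI the gain may be near 4 points (0.70 to 0.74), not 24.

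**The entry rule and change scores.** It is tempting to go further and say that the ISI entry rule makes a change-score test worse than ignoring baseline, because r may fall below 0.5. That does not follow. The 0.5 threshold holds only when the baseline and week-4 SDs are equal, and selection on baseline breaks that equality. The general condition is a regression slope of week-4 on baseline below 0.5, and selection on baseline leaves a linear slope unchanged. Illustration, with assumed bivariate normal scores of unit variance, r = 0.6 before selection, and truncation at the baseline mean: baseline variance falls to 1 − 2/π = 0.363, week-4 variance to 0.36 × 0.363 + 0.64 = 0.771, and r to 0.6 × √(0.363/0.771) = 0.41. The change-score variance is 0.16 × 0.363 + 0.64 = 0.698, about 0.91 of the week-4 variance, so here the change score does better than the raw score.

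**Not all baseline data are assured.** A reader might take every primary measure to have a baseline value. The Protocol states this for the scales, not for actigraphy, although week-4 actigraph data are part of the primary outcome.

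**Scope.** Covariates are often left to a statistical analysis plan, and a separate one may exist. That would weaken the point, but this document says it contains the plan and names a test for the within-patient analysis while leaving the randomised comparison open. It is also true that each candidate test alone is valid, and that naming one model would not settle the several primary measures or the open method for missing data.

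**Conclusion.** The point holds as a badly fixed main analysis with an available improvement. The Protocol leaves the week-4 test and the handling of baseline open, so power is at risk and the test can be chosen after the data are seen. At 50 per arm and a 0.5 SD difference, the cost of an unadjusted test relative to ANCOVA is about 4 to 24 percentage points of power for r from 0.3 to 0.7, possibly near the lower figure for ISI. These figures rest on assumed allocation, effect size, sidedness and correlation. The selection problem was present at every r examined. The text does not support a firmer claim that power is lost, that a change score would be the worst option, or that any single candidate test would be invalid.

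**What to change.** For each scale with a recorded baseline value, replace the general phrase for the week-4 comparison with: a linear model of the week-4 score on randomised arm and the baseline-week score of the same scale (ANCOVA), two-sided 0.05, reporting the adjusted mean difference with its 95% confidence interval; an unadjusted test is a sensitivity analysis only. Apply the same model to actigraphy only if actigraph data are recorded in the baseline week, and state whether they are.

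The cost is one sentence in the Statistical analysis section. The scales need no extra patients, visits or measurements. To remove the selection problem, the change must be made before outcome data are examined by arm.

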Patients with sleep disorders and motor / mental anxiety will be recruited at the Affective section at Psychiatry South West. Patients who are expected to use the chain blankets after assessment by the attending physician will be included after informed consent. All patients who accepted inclusion and who received a chain blanket will be included in the analysis.

Inclusion and exclusion criteria

We intend to recruit patients from Psychiatry Southwest with affective and anxiety diagnoses and/or ADHD, which are simultaneously bothered by sleep disturbance and anxiety/anxiety. Patients are recruited from open and inpatient wards. They should have one of the diagnoses Bipolar Disorder Type I, Type II Bipolar Disorder, Recurrent Depression, Panic Syndrome, Social Phobia, General Anxiety Disorder (GAD) and/or ADHD. They should also have a clinically significant sleep disorder, i.e., a rating of 14 or more on ISI. Exclusion criteria are ongoing drug abuse, consumption of sleep medication beyond recommended levels (> 7.5 mg zopiclone or 10 mg zolpidem) or cognitive problems that make the patient unable to complete the study.

Characteristics of patient material

The examined group will be characterized by age, sex, choice of cover, weight, diagnosis, comorbid diagnosis and duration of disease.

Procedure

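### The one-night analysis set is mislabelled as intention to treat and conflicts with the set given under Patients

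*Protocol*

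**What the plan says.** The protocol defines the analysis set twice.

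- Statistical analysis: "All patients who used the blanket for at least one night will be included in the analysis". The same sentence describes this set as equivalent to intention to treat.
- Project plan, Patients: "All patients who accepted inclusion and who received a chain blanket will be included in the analysis". This rule has no condition on use.

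Four other statements bear on the point.

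- Procedure places randomisation at the start of the second phase, after a baseline week with the usual blanket: "patients are randomized to either get a 6 or 8 kg lining blanket or a lightweight cover of approximately 1.5 kg".
- Purpose describes the control as a chain blanket too: "compared to a light chain blanket (equivalent to placebo) after four weeks of use". The Patients rule can therefore cover both arms.
- Patients adds a condition on enrolment: "Patients who are expected to use the chain blankets after assessment by the attending physician will be included after informed consent".
- Statistical analysis asks patients who discontinue to accept follow-up as if they had completed treatment. Where they agree, their data are analysed as observed.

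**The concern.** Intention to treat means that every randomised patient is analysed in the arm assigned, whatever happens afterwards. Using the blanket for a night is something the patient does after randomisation. A set conditioned on it lacks the property that the label claims.

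The condition could also act unequally. The two kinds of blanket look alike, but one weighs 6 or 8 kg and the other about 1.5 kg, a difference a patient can feel before the first night. If more patients in one arm decline to use the blanket, and those patients differ in outcome, dropping them biases the week-4 comparison that carries the primary outcome. The rule also draws a line that the protocol does not explain: a patient who stops after one night is followed and counted, while one who stops before it is not.

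Because a second rule stands under Patients, the treatment of never-users is not settled in one place.

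**Working it through.** **The two rules side by side**

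| Patient after randomisation | Patients rule | Statistical analysis rule | Intention to treat |
|---|---|---|---|
| Received blanket, used it at least one night | in | in | in |
| Received blanket, never used it | in | out | in |
| Randomised, received no blanket | out | out | in |

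The second row is the contradiction. The third row shows that the Patients rule is not strictly intention to treat either. That row may be empty if blankets are handed over at randomisation. Procedure suggests this ("Randomization and instruction, as well as collection of blankets after four weeks of use, will be carried out by a person") but does not state it.

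**Size of the possible bias**

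The protocol has no figure to reproduce here. It gives a total of about 100 patients (Power Calculation). Everything else is assumed: an equal split of 50 per arm, SD 1, no true effect, a pooled two-sided t-test at 0.05, and a proportion q of potential never-users in each arm whose outcome differs by δ SD. In the worst case they are removed from one arm only.

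Bias = −q × δ. The standard error of the difference is √(2/50) = 0.2 SD. Simulation with 400,000 trials per setting (Monte Carlo standard error 0.0003 to 0.0004) gave:

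| q | Type I error, δ = 0.5 | Type I error, δ = 1 | Bias in SD (δ = 0.5 / 1) |
|---|---|---|---|
| 2% (1 of 50) | 5.0% | 5.2% | −0.010 / −0.020 |
| 4% (2 of 50) | 5.1% | 5.4% | −0.020 / −0.040 |
| 5% | 5.1% | 5.7% | −0.025 / −0.050 |
| 10% (5 of 50) | 5.6% | 7.5% | −0.050 / −0.100 |

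Hand check at q = 5%, δ = 1: the bias is 0.05/0.2 = 0.25 standard errors, so the error is about Φ(−1.96 + 0.25) + Φ(−1.96 − 0.25) = 0.044 + 0.014 = 5.7%.

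The result depends on imbalance. At q = 10% and δ = 1, if the other arm also loses 80% of its potential never-users the error is 5.1%. If it loses all of them, it is 5.0%.

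**Power when all randomised patients are analysed**

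At 50 per arm, 90% power corresponds to a difference of 0.6548 SD. Suppose a proportion q of the weighted arm never uses the blanket and gets no effect. The mean difference is then 0.6548 × (1 − q): 0.642 at 2%, 0.622 at 5% and 0.589 at 10%.

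| q | Power, never-users otherwise alike | Power, potential never-users in both arms 1 SD worse |
|---|---|---|
| 2% | 88.8% | about 87.5% |
| 5% | 86.9% | about 84% |
| 10% | 83.1% | about 77% |

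The first column uses the noncentral t distribution and the second uses simulation. The second matches the 1 SD gap in the bias table, because the same patients also add spread to the outcome.

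**The case against.** The strongest reply is about weight. The protocol enrols patients whom the physician expects to use the blanket, which points to the low end of the table, where type I error is 5.0% to 5.4% at 2% to 4% never-use. The 7.5% figure needs 10% never-use, all exclusions in one arm and a 1 SD gap, and the protocol supports none of these. This stands, and it keeps the severity down.

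A second reply is that both sentences say who is included and neither says who is excluded, in a text translated from Swedish. On that reading there is no conflict, but the one-night condition would then do nothing. A reader might also apply the Statistical analysis rule as the more specific one. That would settle the contradiction in practice but leave the wrong label.

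A third reply is that the one-night rule stands in the same sentence as the label, so nothing is hidden. That is fair: the protocol does not show that a report would omit the rule.

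A reader might infer more from the text than it supports. The final visit is described as coming after four weeks of blanket use, which could be taken to bar never-users from the primary assessment. The phrase reads as a time marker. Taken literally it would also bar discontinuers, whom Statistical analysis expressly follows up. Nor do the weekly calls depend on use: "They are followed up by telephone every week".

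**Conclusion.** The point holds as a mislabel and a contradiction, whatever the number of patients affected. The one-night set is a modified set, and the protocol gives two different answers for a patient who received a blanket and never used it. Neither rule is strictly intention to treat.

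The numerical effect is probably small: type I error of about 5.0% to 5.7% at 2% to 5% never-use with a 0.5 to 1 SD gap, and 7.5% only at 10% with 1 SD. These figures assume 50 per arm and exclusions from one arm only. The protocol gives no never-use rate, no difference between arms and no link to outcome, so the size and direction of any bias are unknown. It would be tempting to conclude that the trial's false-positive rate is materially inflated, but the document does not support that. Severity is minor to modest.

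**What to change.** Replace both sentences with one rule: *All randomised patients are analysed in the arm to which they were randomised, whether or not the blanket was used.* State that the planned follow-up of discontinuers also covers patients who never used the blanket. Keep the one-night set only as a sensitivity analysis, named as a modified set. Adopting the Patients sentence alone would not be enough, because it omits anyone randomised who received no blanket.

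The follow-up clause is needed because rewording removes the bias only if week-4 data are obtained. At 10% one-sided never-use and a 1 SD gap, type I error is 7.5% if no never-users supply data, 5.6% if half do and about 5% if all do.

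The cost is one sentence in place of two, one clause, and a few extra week-4 ratings. Use is already to be recorded: "At the telephone interview information about how they used the blanket will be gathered". There is also some dilution. Power of 90% falls to about 89%, 87% and 83% at 2%, 5% and 10% never-use in the weighted arm if never-users do not otherwise differ. It falls to about 87.5%, 84% and 77% if potential never-users in both arms do 1 SD worse. That is the usual price of estimating the effect of assignment and no reason to keep the present label.
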